14.1. DERIVATIONS

Compliance is calculated as below and will be rounded to 1 decimal place:

$$\begin{aligned} \text{Compliance per period (\%)} \\ &= \frac{\text{Number of days saline irrigation was completed during washout/treatment period}}{\text{Duration of washout/treatment period (days)}} \\ &\times 100 \end{aligned}$$

- Duration of washout period is defined as:
-

Duration of washout period (days) = washout stop date – washout start date + 1

- Duration of treatment period is the same as the duration of exposure as noted in Section 13.1 but will be converted from weeks to days (multiply by 7).

15. EFFICACY OUTCOMES

15.1. PRIMARY EFFICACY

15.1.1. PRIMARY EFFICACY ENDPOINT AND DERIVATION

The primary efficacy endpoint is CFBL in CS7DA4S score at Week 4. The 4 CS cardinal symptoms are:

- nasal blockage/obstruction/congestion
- facial pain/pressure
- reduction/loss of sense of smell
- anterior/posterior nasal discharge.

Each symptom is scored on a 4-point scale and is collected on ePRO:

- 0 = none
- 1 = mild
- 2 = moderate
- 3 = severe

The CS7DA4S score is calculated as:

- Add together the four individual symptom scores per day as recorded by the subject to derive the total daily score
 - Total daily scores will only be calculated in cases where all four individual symptom scores are available
- Calculate the average of the total daily scores across the 7 days leading up to and including this visit.
This is the CS7DA4S score at the relevant visit
 - Subject is considered to have sufficient data available to calculate the CS7DA4S score at any given

timepoint if the total daily score is available for at least 5 of the total 7 days

- CS7DA4S scores will be rounded to 1 decimal place

The change from baseline in CS7DA4S at Week 4 will be calculated as detailed in Section 6.7.

15.1.2. MISSING DATA IMPUTATION METHODS FOR PRIMARY EFFICACY ENDPOINT

The primary analysis will not include any missing data imputation methods. The primary analysis of the primary efficacy endpoint will include subjects in the ITT analysis set with available CS7DA4S data at Baseline and Week 4 visit.

15.1.3. PRIMARY ANALYSIS OF PRIMARY EFFICACY ENDPOINT

The CFBL for CS7DA4S at Week 4 will be analyzed using the ITT analysis set. The following analysis will be performed for the CFBL CS7DA4S score at Week 4:

- Summary statistics for the Baseline CS7DA4S score, the Week 4 CS7DA4S score and the CFBL at Week 4
- An ANCOVA model for CFBL at Week 4. The ANCOVA model will include the baseline CS7DA4S score as a covariate, treatment group and the randomization stratification variables (nasal allergy, nasal polyps) as fixed effects.

Each hypothesis as described in Section 7.8 will be tested at a one sided 0.05 alpha level of significance by the ANCOVA model. The LS means and SE of each treatment group, the LS mean difference of each LYR-210 procedure against the Sham procedure and their SEs, 90% CIs, and p-values estimated by the model will also be provided.

15.1.4. SENSITIVITY ANALYSIS OF PRIMARY EFFICACY ENDPOINT

The following sensitivity analyses to the primary analysis of the primary endpoint will be performed:

Sensitivity to the analysis set

The primary analysis of the primary efficacy endpoint will be repeated for the PPAS.

Sensitivity analyses to missing data

- LOCF single imputation method:
 - The CS7DA4S will be calculated as described in Section 15.1.1 for baseline, Week 1, Week 2, Week 3

and Week 4

- If Week 4 CS7DA4S score is missing, then the last available post baseline CS7DA4S prior to Week 4 will be carried forward and will be used as the Week 4 CS7DA4S score and the same analysis as for the primary analysis of the primary efficacy endpoint will be repeated (refer to Section 15.1.3).
- Multiple imputation will be implemented using 3 steps:
 - First, intermittent missing CS7DA4S data will be imputed under the missing at random (MAR) assumption using a multivariate joint Gaussian imputation model and the Monte Carlo Markov Chain (MCMC) method. A separate imputation model will be estimated for each treatment group separately. The imputation models will include the baseline CS7DA4S values as a covariate and the stratification variables and weekly CS7DA4S (Weeks 1 to 4) as factors. The MAR mechanism assumed that subjects have unobserved values in line with similar subjects with available data in their treatment group, taking into account their values observed prior to the weeks with missing data. The MAR assumption is reasonable for the Sham patients as it accounts for the trial effect while no active treatment is taken. It is also a reasonable assumption for the LYR-210 subjects as subjects will remain on randomized treatment while intermittent missing data may occur and thus, may be modeled based on similar subjects from their randomized treatment group. The MCMC method will be used with a random seed number of 2575, multiple chains, a burn-in of 200 iterations, and non-informative prior. During this step, 50 imputed datasets will be created.
 - Second, for each of these 50 imputed datasets, monotone missing weekly CS7DA4S data will be imputed using sequential linear regression multiple imputation approach also using a MAR approach, where a separate regression model will be estimated for imputation of each post-baseline timepoint (i.e., Weeks 1, 2, 3, and 4). Each regression model will include the treatment group, region, the two stratification variables, and all previous weekly CS7DA4S scores (Baseline and Weeks 1 to Week 4), as appropriate. In other words, to impute Week 1, the model will include the treatment group, region, the two stratification variables and baseline CS7DA4S scores. Similarly, to impute Week 2, the model will include the treatment group, region, the two stratification variables, baseline CS7DA4S scores, and CS7DA4S scores at Week 1 (observed and imputed values). Missing CS7DA4S scores at Weeks 3 and 4 will be similarly imputed, one after the other. The random seed number for this step will be 210. No rounding or range restrictions will be applied to imputed weekly average values.
 - Finally, each of the 50 imputed datasets will be analyzed using the following method: change from baseline in CS7DA4S score at Week 4 will be calculated based on the observed and imputed data and analyzed using the ANCOVA model as described in Section 15.1.3. For each LYR-210 dose group, results from the analysis of each imputed dataset i.e., LS mean differences between treatment groups and their SEs, will be combined using PROC MIANALYZE in SAS as per Rubin's rule (Rubin, 1987) to produce a

pooled estimate of the LS mean difference between treatment groups and a pooled estimate of its SE. From these pooled estimates, one t-test statistic and its p-value, assessing whether the null hypotheses in Section 7.8 can be rejected, will be calculated and presented for each LYR-210 dose vs. Sham.

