#### **10.6.1.1 Handling of Missing Data**

The primary efficacy endpoint analysis will be performed based on subjects in the ITT analysis set with available CS7DA4S data at Baseline and Week 4 visit. At each of these visits, a subject is considered as having an available (NON-missing) CS7DA4S score if the daily ePRO score is available (NON-missing) for at least 5 of the preceding 7 days prior to the time point.

For the secondary analyses based on all subjects in the ITT analysis set regardless of available data status, two imputation approaches will be carried out for subjects who have missing Week 4 CS7DA4S data: (a) Last observation carried forward (LOCF) single imputation method; and (b) multiple imputation.

LOCF will be carried out as follows: the CS7DA4S score at each visit will be calculated in a similar manner as described above for the Baseline and Week 4 visits (i.e., 7-day average scores of the 4 CS cardinal symptoms at that visit). If Week 4 CS7DA4S is missing, then the last available CS7DA4S calculated at a post-baseline visit prior to Week 4 will be carried forward and be used as the Week 4 CS7DA4S.

The multiple imputation approach will be carried out as follows:

- A. Assuming the missing CS7DA4S pattern at Baseline, Weeks 1, 2, 3 and 4 will not be exactly monotone across visits through Week 4, then a non-monotone missing pattern in CS7DA4S will be imputed 50 times to make 50 copies of a dataset with a monotone missing CS7DA4S data pattern; the Monte Carlo Markov Chain approach will be used for this imputation.
- B. For each of these 50 imputed datasets, missing CS7DA4S at Week 4 will be imputed using the monotone linear regression approach: the imputation regression model will include treatment group, study center/region, randomization strata variables, CS7DA4S measured at Baseline and Weeks 1, 2, and 3 scores, and Baseline subject and demographic characteristics that will be fully specified in the SAP.
- C. The above-mentioned analysis of covariance comparing treatments on the mean primary endpoint will be carried out on each of the 50 imputed datasets. The estimate of the treatment differences in least square means vs. Sham and their standard errors from each imputed dataset will be combined across the imputed datasets using PROC MIANALYZE in SAS in order to

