3.3. CHANGES TO ANALYSIS FROM PROTOCOL

- The Study Design Schematic was presented in the protocol in Section 4.1. The protocol version 8 did not include the LYR-210 7500 µg treatment arm. An updated version that differs from the protocol is included in the SAP in Section 3.1.
- The endpoint regarding the reduction in subjects' need for specified concomitant medications and medical or surgical treatment for CS will not be analyzed as the data was not collected.
- Section 10.1 of the protocol defines the safety analysis set (SAF) as consisting of all randomized subjects who received the study treatment or treatment attempt on Day 1. For the purposes of the SAP, this has been re-

defined to remove the randomization criteria. It is possible a subject may receive treatment without being formally randomized. Hence the SAF should not contain the randomization restriction.

- Section 10.2 of the protocol states that subject disposition will be summarized for the Intention-to-Treat analysis set (ITT). For the SAP this has been updated to use the All Subjects Consented analysis set (CONS). The ITT for this study includes the condition that subjects will have a post-Day 1 assessment. It is recommended that disposition summaries include all subjects enrolled into the study. Restricting to the ITT will lead to an incomplete summary of subject disposition.
- Section 10.6.1.1 of the protocol describes the one missing value analysis approach as multiple imputation with treatment group as an independent variable in the multiple imputation model. This approach will be conservatively adjusted to apply control-based multiple imputation.
- Section 10.6.1.2 of the protocol describes the model to assess treatment effect across study regions but excludes the stratification variables. The model for the SAP includes the stratification variables. Per ICH E9 all statistical tests/models should be adjusted for any stratification variables.
- Section 10.6.1.2 of the protocol states that subgroup analysis will be performed to assess the treatment effect for the subgroups outlined in Section 7.6 of this SAP and the same model as the region analysis will be used. Due to the small sample size, for the purpose of the SAP one ANCOVA model will be fitted per subgroup to keep the model parsimonious.

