15.2.3. MISSING DATA IMPUTATION METHODS FOR SECONDARY EFFICACY ENDPOINTS

15.2.3.1. Missing Data Imputation Methods for Key Secondary Efficacy Endpoints

For the primary analysis of the CFBL in CS7DA4S score at Week 24 key secondary efficacy endpoint, LOCF and multiple imputation will also be used to impute missing data for sensitivity analyses (refer to Section 15.1.4).

For bilateral Zinreich score and time-to-treatment failure, no imputation for missing data will be performed.

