15.2.4. ANALYSIS OF KEY AND OTHER SECONDARY EFFICACY ENDPOINTS

15.2.4.1. Analysis of CFBL in CS7DA4S Individual and Total Scores at Weeks 8, 12, 16, 20 and 24

The analysis of the CFBL in CS7DAS total score will be conducted using an ANCOVA model as per Section 15.1.3. Week 24 is considered a key secondary endpoint, while Weeks 8, 12, 16, and 20 are considered as non-key secondary endpoints and all other visits as exploratory endpoints.

Additionally, the 7-day average score of nasal blockage/obstruction/congestion, reduction/loss of sense of smell, facial pain/pressure and anterior/posterior nasal discharge at Weeks 1, 2, 3, 4, 8, 12, 16, 20, 24 will be analyzed as per Section 15.1.3.

This analysis will be repeated for the ITT and PP analysis sets.

The same three sensitivity and supportive subgroup analyses as for the primary endpoint as detailed in Sections 15.1.4 and 15.1.5.2 will be repeated for the CS7DA4S total scores at all Weeks. Furthermore, the analysis of the CS7DA4S total score at all Weeks by CSsNP and CSwNP subgroups will be repeated with missing data imputed as per Section 15.1.2.

For all other endpoints, the sensitivity analyses based on the PP analysis set and based on the ITT analysis set but with missing data imputed based on LOCF will be performed. That is, no sensitivity analysis based on the ITT analysis set with missing data imputed based on the multiple imputation method will be performed for the other secondary efficacy endpoints.

Additionally, a plot of the LS means and SE for CFBL for CS7DA4S total and individual symptom scores at each timepoint up to Week 24 and Week 48 will be provided for the primary and final data analysis, respectively.

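### SAP 3.3 declares control-based multiple imputation, but SAP 15.1.4 specifies MAR imputation with treatment group in every model

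*SAP*

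**What the plan says.** Protocol 10.6.1.1 plans multiple imputation as a secondary analysis of CS7DA4S at Week 4. Its step B is a monotone regression in which "the imputation regression model will include treatment group, study center/region, randomization strata variables" and the earlier scores are predictors.

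SAP 3.3, which lists where the SAP departs from the protocol, names the treatment term in that model and then states: "This approach will be conservatively adjusted to apply control-based multiple imputation".

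SAP 15.1.4 is the only place where the SAP specifies the method. Step 1 fills intermittent gaps by MCMC under MAR, separately in each arm. In step 2, "monotone missing weekly CS7DA4S data will be imputed using sequential linear regression multiple imputation approach also using a MAR approach", and "Each regression model will include the treatment group, region, the two stratification variables, and all previous weekly CS7DA4S scores". Step 3 fits the ANCOVA to each completed dataset and pools by Rubin's rules.

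For Week 24, SAP 15.2.3.1 says "LOCF and multiple imputation will also be used to impute missing data for sensitivity analyses" and refers back to 15.1.4. SAP 15.2.4.1 does the same for CS7DA4S at the other weeks: "The same three sensitivity and supportive subgroup analyses as for the primary endpoint" are repeated. For the primary analysis, SAP 15.1.2 says: "The primary analysis will not include any missing data imputation methods".

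**The concern.** The two sections describe different analyses. A programmer following 15.1.4 runs MAR imputation. A reader relying on 3.3 believes that a conservative, sham-referenced check was done.

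Under step 2 as written, a LYR-210 subject with monotone missing data is imputed in line with LYR-210 subjects who had similar earlier scores. The other two checks do not fill the gap. The per-protocol repeat drops subjects without a Week 4 change score, and LOCF carries a subject's own last score forward. Nothing in the plan asks whether the result survives if LYR-210 subjects who stop providing data respond like sham.

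The SAP's justification of MAR for active subjects does not reach these cases. It reads "It is also a reasonable assumption for the LYR-210 subjects as subjects will remain on randomized treatment while intermittent missing data may occur", which concerns intermittent gaps. No reason is given for monotone gaps, which can follow early depot removal or withdrawal. Because 15.2.3.1 and 15.2.4.1 reuse the method, the gap carries to Week 24 and the other CS7DA4S time points.

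**Working it through.** **Text.** For the plan to be control-based, some step would have to estimate the model from Sham alone, omit the treatment term, or apply a reference or delta shift.

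| Place | Mechanism | Treatment in model |
|---|---|---|
| Protocol 10.6.1.1, step B | monotone regression | yes |
| SAP 3.3 | control-based, replacing the above | the feature said to be changed |
| SAP 15.1.4, step 1 | MAR, intermittent gaps | fitted per arm |
| SAP 15.1.4, step 2 | MAR, monotone gaps | yes, every regression |
| SAP 15.1.4, step 3 | ANCOVA and Rubin's rules | no shift applied |

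Step 2 is close to the protocol's step B: it uses region rather than centre/region and leaves out further baseline characteristics. SAP 7.3, 15.1.2, 15.2.3, 15.2.4.1 and 15.3.2 also deal with missing data, and none supplies a control-based step. The other method changes listed in 3.3 are carried into the body: safety set (5.4), disposition (9), strata in the region model (15.1.5.1), one ANCOVA per subgroup (15.1.5.2), SNOT-22 mean imputation (15.2.2.3) and the retained GEE interaction (15.3.3). The imputation entry is the exception.

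**Planning inputs (SAP 7.1).** Means are -1.30 and -3.00, so the difference is -1.70. SD is 2.4, with 21 evaluable per arm and one-sided 0.05. Noncentrality is 1.70 / (2.4 x sqrt(2/21)) = 2.295. Power is 74.2% by the normal approximation and 73.0% by noncentral t on 40 df, so the stated 73% reproduces. The dropout allowance is 6/69 = 8.7% to 9/72 = 12.5%.

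**Illustrative size at Week 4.** The following are assumptions, not in the documents: equal variance and correlation rho between all weekly scores (0.5 to 0.8), equal missing fraction m in each arm, and the onset profile. With baseline and k earlier weekly scores as predictors, each sham-fitted coefficient is rho / (1 + k x rho), so

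expected effect = (1 - m) x (-1.70) + m x [rho / (1 + k x rho)] x (sum of effects at the observed weeks).

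Example: m = 0.125, k = 3, rho = 0.5, full effect from Week 1. The coefficient is 0.5/2.5 = 0.2 and the sum is 3 x (-1.70) = -5.10. The result is 0.875 x (-1.70) + 0.125 x 0.2 x (-5.10) = -1.4875 - 0.1275 = -1.615.

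| Case | m = 8.7% | m = 12.5% |
|---|---|---|
| MAR with treatment term | -1.70 | -1.70 |
| Sham-fitted, no earlier weekly score | -1.552 | -1.488 |
| Sham-fitted, Weeks 1-3 seen, full effect from Week 1 (rho 0.5; 0.8) | -1.641; -1.657 | -1.615; -1.637 |
| Sham-fitted, Weeks 1-3 seen, linear build-up to Week 4 (rho 0.5; 0.8) | -1.597; -1.604 | -1.551; -1.562 |

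**Simulation check.** Settings: 24 per arm, 400 runs, rho 0.7, linear build-up, dropout spread over Weeks 1-4. At 12.5% dropout, MAR gave -1.70 and the sham-only model -1.53 (Monte Carlo SE about 0.03), inside the range above.

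**Week 24.** The documents give no missing rate or effect there. If -1.70 also applied, each 10 percentage points missing would move the estimate by at most 0.10 x 1.70 = 0.17.

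**The case against.** The case for treating this as minor has several parts.

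- **Stakes.** The primary analysis is observed-case, SAP 7.8 calls the study exploratory and gives only nominal p-values, and no decision rule uses the imputed result. The largest Week 4 shift, 0.15 to 0.21, is under a third of a simulated standard error of about 0.66 to 0.71. This stands and limits the consequence.
- **Only one version can be programmed.** SAP 15.1.4 gives seeds, burn-in and predictors, whereas 3.3 gives one sentence and names no control-based variant. MAR would probably be run under a wrong label. That is likely, but it means the declared conservative check would be missing.
- **Missing fraction.** The 8.7% to 12.5% is an enrolment allowance. The ITT set excludes subjects without any post-Day 1 assessment, so the row with no earlier weekly score is an extreme case. Diary gaps could push the fraction the other way. This stands as a limit on the illustration.
- **Correlation model.** With baseline confined to 7-12, its SD cannot exceed 2.5. Equal variances with SD of change 2.4 imply a score SD of 2.4/sqrt(2 x 0.2) = 3.79 at rho 0.8, which is impossible for baseline. If baseline adds nothing given Weeks 1-3, the coefficient becomes rho / (1 + (k - 1) x rho), and the full-effect result at 12.5% is about -1.65 to -1.68. The shift is then smaller still.
- **Week 24.** SAP 15.1.4 names only Weeks 1 to 4, so the Week 24 imputation model is not actually written out. This is true, and the fix should cover it.

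These points bear on size. None removes the contradiction.

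**Conclusion.** The concern holds. SAP 3.3 is current text describing the SAP's own method, not a record of superseded wording, and the multiple imputation in SAP 15.1.4 lacks the control-based property that 3.3 claims for it. As specified, no sensitivity analysis tests a sham-like response in LYR-210 subjects with monotone missing data.

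The conclusion rests on the text alone. The figures only show that the two methods differ and that the Week 4 difference is modest: a shift of about 0.04 to 0.21 points from -1.70 under the tabulated assumptions, possibly less if baseline predicts little. The Week 24 size is unknown. The point should be fixed, but it does not threaten the primary result.

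**What to change.** Reconcile SAP 3.3 and 15.1.4 before unblinding; afterwards the choice between methods could be driven by the results.

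**Preferred, following 3.3.** In step 2, impute monotone-missing values by sequential regression estimated in Sham subjects only, with no treatment term, using baseline and all earlier CS7DA4S scores (for example PROC MI with an MNAR MODEL statement and MODELOBS restricted to Sham). Keep step 1 under MAR for intermittent gaps. Keep the present MAR version as a separately labelled sensitivity analysis. Apply the same approach at Week 24 and list the visits that enter that model. Label the control-based version a stress test, because a score is also missing when fewer than 5 of 7 diary days are complete, even with the depot in place.

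Keep other covariates few. Adding region and two strata to the intercept, baseline and three weekly scores gives eight coefficients, with only about 21 to 24 sham subjects to estimate them.

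**Alternative, if MAR was intended.** Correct the 3.3 entry so that the method is not described as control-based or conservative. A further non-MAR analysis would then be optional.

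**Cost.** SAP wording and a few SAS statements, plus a slightly less favourable and less precise sensitivity estimate. In simulation (1000 trials, 24 per arm, 3 missing per arm, Weeks 1-3 observed, full effect, rho 0.5), the mean SE rose from 0.66 under MAR to 0.68 with baseline and earlier scores only, and rejection fell from 0.83 to 0.80. With region and strata also fitted, the SE rose from 0.66 to 0.71 and rejection fell from 0.81 to 0.75.

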7.7. STATISTICAL TESTS

The default significance level will be 5% and all tests will be one-sided, unless otherwise specified in the description of the analyses. Two-sided 90% CIs will be presented for all outputs were relevant.

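### The SAP does not state the reference degrees of freedom for the pooled multiple-imputation t-test, and the 1987 rule it cites ignores the ANCOVA's residual degrees of freedom; the effect is minor

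*SAP*

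**What the plan says.** The primary analysis (SAP 15.1.2 and 15.1.3) is an ANCOVA on ITT subjects with observed Baseline and Week 4 scores, without imputation. Its terms are baseline score, treatment group, nasal allergy and nasal polyps. Each dose–sham hypothesis "will be tested at a one sided 0.05 alpha level of significance by the ANCOVA model".

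Multiple imputation is one of the sensitivity analyses in SAP 15.1.4. On the number of imputations: "During this step, 50 imputed datasets will be created". In the third step each completed data set is analysed with the same ANCOVA, and the LS mean differences and "their SEs, will be combined using PROC MIANALYZE in SAS as per Rubin's rule (Rubin, 1987"). The test follows: "From these pooled estimates, one t-test statistic and its p-value, assessing whether the null hypotheses in Section 7.8 can be rejected, will be calculated". Protocol 10.6.1.1 has the same plan; the estimates and standard errors "will be combined across the imputed datasets using PROC MIANALYZE in SAS".

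Neither document names a reference df, a value for the EDF option or a small-sample adjustment. The imputation step promises an estimate, a standard error, a t statistic and a p-value. It does not mention an interval, which would come only from the general rule in SAP 7.7: "Two-sided 90% CIs will be presented for all outputs were relevant".

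The same imputation is reused for the Week 24 score (SAP 15.2.3.1) and for other endpoints based on CS7DA4S (SAP 15.2.3.2 and 15.2.4.1).

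**The concern.** A t-test needs df. The rule that the SAP cites takes them from the number of imputations and the fraction of missing information alone, and treats the complete-data df as infinite. That is harmless in a large trial. Here the ANCOVA has about 60 residual df even if nothing is missing.

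Followed literally, the sensitivity analysis would have a more lenient reference distribution than the ANCOVA it is meant to check. With an identical estimate and standard error, the imputation p-value would be smaller for no reason connected with the data. A missing-data check should not gain precision in this way. What is at stake is how closely the imputation p-values can be compared with the primary ones; the primary result itself is not affected.

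**Working it through.** **Inputs from the documents**
- m = 50 imputations (SAP 15.1.4).
- One-sided 0.05 per hypothesis (SAP 15.1.3).
- N = 63 evaluable subjects, 21 per arm (SAP 7.1), to about 70 planned (SAP 3.1).
- ANCOVA parameters (SAP 15.1.3): intercept 1 + baseline 1 + treatment 2 + allergy 1 + polyps 1 = 6. The complete-data df is therefore ν₀ = N − 6, that is 57 for N = 63 and 64 for N = 70.

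**Assumed input**
- λ, the fraction of missing information, is not in the documents. The dropout allowance of 6 to 9 subjects gives 6/69 = 8.7% to 9/72 = 12.5%. Earlier weekly scores would probably bring λ below the dropout rate. The range shown is 0.02 to 0.30.

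**The plan's own figure.** SAP 7.1 states 73% power for a difference of −1.30 − (−3.00) = 1.70, SD 2.4 and 21 per arm. The noncentrality is 1.70 / (2.4 × √(2/21)) = 2.295. A noncentral t calculation gives 73.0% with 40 df and 73.3% with 57 df, so the figure reproduces for a single dose–sham comparison. With the normal critical value in place of t it would read 74.2%, about one point higher.

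**Formulas**
- 1987 rule: ν_R = (m − 1)/λ² = 49/λ².
- Small-sample adjusted (Barnard–Rubin) df: ν_adj = 1 / (1/ν_R + 1/ν_obs), with ν_obs = [(ν₀ + 1)/(ν₀ + 3)] × ν₀ × (1 − λ).
- Actual one-sided level = P(t with ν_adj df > 95% point of t with ν_R df).

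**One case in full (N = 70, λ = 0.10).** ν_R = 49/0.01 = 4900. ν_obs = (65/67) × 64 × 0.90 = 55.9. ν_adj = 1/(1/4900 + 1/55.9) = 55.3. The critical values are 1.645 unadjusted and 1.673 adjusted. The actual level is 0.0528, and the adjusted 90% interval is 1.7% wider.

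**Range**

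| N | λ | ν_R | ν_adj | critical value, 1987 rule | critical value, adjusted | actual one-sided level | adjusted 90% CI wider by |
|---|---|---|---|---|---|---|---|
| 70 | 0.02 | 122,500 | 60.8 | 1.645 | 1.670 | 0.0526 | 1.6% |
| 70 | 0.10 | 4,900 | 55.3 | 1.645 | 1.673 | 0.0528 | 1.7% |
| 70 | 0.30 | 544 | 40.2 | 1.648 | 1.684 | 0.0536 | 2.2% |
| 63 | 0.02 | 122,500 | 54.0 | 1.645 | 1.674 | 0.0529 | 1.8% |
| 63 | 0.10 | 4,900 | 49.1 | 1.645 | 1.677 | 0.0532 | 1.9% |
| 63 | 0.30 | 544 | 36.0 | 1.648 | 1.688 | 0.0541 | 2.5% |

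**Against the ANCOVA with nothing missing.** Its critical value is 1.672 with 57 df and 1.669 with 64 df. The 1987 reference (1.645 to 1.648) is more lenient than either.

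**Effect on a reported p-value.** At λ = 0.10, a p of 0.040 becomes 0.043, and 0.048 becomes 0.051. The p-value that lands exactly on 0.05 after adjustment runs from 0.0474 (N = 70, λ = 0.02) to 0.0460 (N = 63, λ = 0.30). Only reported values between about 0.046 and 0.050 could change sides.

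**The case against.** The strongest reply is that the SAP is silent on df rather than wrong. A reader might infer that the plan excludes the complete-data df. It does not: the 1987 citation is attached to the pooled estimate and its standard error, the df are left open, and a programmer who supplied EDF would comply with both documents. This stands. What remains is that the only rule named does not use the residual df, and that a section fixing both seeds, the burn-in, the prior and the number of imputations should not leave to choice an option that alters the p-value.

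A reader might also infer that the imputation results would be materially too favourable. The figures do not support that: the excess is about 0.3 to 0.4 percentage points of alpha. The imputation is a sensitivity analysis, the primary analysis imputes nothing (SAP 15.1.2), and all p-values are nominal (SAP 7.8). No decision rule depends on it.

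Finally, a reader might expect a much larger distortion in small polyp subgroups. The documents do not clearly specify this imputation there. SAP 15.2.4.1 refers the imputed subgroup analysis to 15.1.2, which contains no imputation method, and SAP 15.3.2 rules out missing-data methods for exploratory analyses. No subgroup figure is claimed here.

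**Conclusion.** The point holds as a minor gap in specification. Following the cited rule with no EDF gives a one-sided level of about 5.3 to 5.4% for a nominal 5%, and 90% intervals about 1.5 to 2.5% too narrow wherever SAP 7.7 leads to their being shown. The direction is anti-conservative. The size rests on m = 50, ν₀ = 57 to 64 and the assumed λ of 0.02 to 0.30, and it changes little across that range. It touches the imputation analyses at Week 4 and those that reuse the method. The primary ANCOVA and every pooled point estimate and standard error are unaffected.

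**What to change.** Add to the third imputation step in SAP 15.1.4: *PROC MIANALYZE will be run with EDF equal to the residual degrees of freedom of the ANCOVA fitted (N minus 6 for the full model), so that the small-sample adjusted degrees of freedom are used for the p-value and for any 90% CI.* State that this applies wherever the imputation is reused, including the Week 24 score. Tying EDF to the model fitted matters because a model without the polyp term (SAP 15.3.3) has 5 parameters, so its residual df is N minus 5.

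The cost is one sentence and one SAS option. The imputation p-values become slightly larger, so the change cannot favour the product.
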